After screening, participants attended a baseline assessment visit where they will again be screened for eligibility. If eligible, participants were given the opportunity to provide written informed consent.

5) Procedure:

Those who consented to participation in this study completed a baseline assessment with a study coordinator. At the baseline assessment, participants completed a self-report questionnaire for demographic information and symptom severity, and completed baseline psychosocial surveys using the REDCap electronic data capture system, a secure data capture program available through Albert Einstein College of Medicine. Participants were given access to the REDCap Headache Diary Application for the duration of the four-week baseline assessment. If the participant did not have an iPhone or iPod touch, an iPod Touch was provided. The study coordinator provided education and orientation to the use of the headache diary application as well as the reminder system that will guide participants to optimal completion. At the conclusion of the 4-week baseline assessment period, all participants will complete psychosocial measures again via REDcap through an

email reminder.

Study participants received up to \$70 for participating in the study.

Participants who continue to meet study inclusion/exclusion criteria will be randomized to either the MBCT-M or WL/TAU group. We will use a randomization procedure stratified by episodic vs. chronic migraine based on headache days/month recorded in the daily headache diary. A statistician otherwise unrelated to the study used a computerized random number generator to randomize participants in random blocks of 2, 4, and 6 participants stratified by headache days/month (cut off score of 15).

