During the 8-week treatment phase, participants randomized to the MBCT-M intervention group attended 8 weekly individual 75-90 minute sessions using a treatment protocol adapted from the MBCT for Chronic Headache Pain manual by [name]., and [name]. Each session included education, cognitive exercises designed to demonstrate how to think mindfully, and in-vivo mindfulness meditation practice designed to help participants systematically gain mindfulness skills throughout the course of treatment. Participants were given “homework,” including formal mindfulness meditation and informal mindful awareness exercises, labeling thoughts, identifying warning signs for stress and migraine, and planning nourishing activities, in between sessions. Homework was assigned each week, and participants were expected to develop a daily formal mindfulness practice (body scan meditation, seated meditation, breathing meditation). Participants were provided with a course manual, reading materials, and audio recordings to facilitate meditation practice. The weekly sessions were conducted by a clinical psychology student who had completed his or her master’s level training in the clinical psychology, health emphasis Ph.D. program at Ferkauf Graduate School of Psychology. All therapists completed training conducted by [name], who developed the MBCT for Chronic Headache Pain manualized treatment. The doctoral level students received clinical supervision from licensed and credentialed clinical psychologists. During the eight weeks of intervention, participants randomized to the MBCT intervention group continued to complete daily headache diary and record daily formal mindfulness practice for eight weeks. All sessions were audio-recorded and coded for treatment fidelity by two independent raters. Participants randomized to the WL/TAU group did not take the headache diary for the 8 week treatment period.

At the conclusion of the 8-week treatment period, all participants (in both the MBCT-M group and the WL/TAU group) completed headache diaries for 4 weeks. At the conclusion of the four weeks, participants completed one final set of psychosocial measures through the REDCap electronic data capture system. At this point, participants in the WL/TAU group were offered participation in MBCT-M.

Participants randomized to the MBCT group were asked to complete the psychosocial measures 6 months after completion of MBCT through the REDCap electronic data capture system.

Measures

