Measures include the following:

Baseline Survey

We will ask demographics questions pertaining to age, gender, race and ethnicity, as well as validated questions about headache symptoms (AMPP diagnostic module). The latter will help investigators determine an International Classification of Headache Disorders – 3 beta headache diagnosis for each participant.

Headache Diary

Via the iPod Touch/Diary REDCap application, a daily headache diary will assess:

- Headache Day: Number of days on which headache was reported in a month.

- Headache Severity: Day-level headache severity with response options including 0 (None), 1 (Mild), 2 (Moderate), 3 (Severe). Average headache severity will be aggregated by month.
- Migraine Disability Index: (MIDI) a four-item scale that assesses disability related to four domains (Family and Home, Recreation, Social Activity, Job/Occupation). For each domain, an 11-point Likert scale allows for possible ratings of 0 (not at all) to 10 (totally). The four ratings are averaged; the final score is in the 0-10 range with higher scores indicating higher disability. Average day-level migraine disability (MIDI) score will be aggregated by month.

Psychosocial Surveys

- The Migraine Disability Assessment (MIDAS; primary outcome) is a 5-item, self-report instrument measuring disruption experienced due to migraine. Items target role functioning and ask about lost days of house-work, job-work, and non-work activities. Each item is an open question, allowing entry of number of days lost over 90 days. Total scores range from 0-450, and are categorized as <21 (Low Disability) and ≥21 (Severe Disability).
- The Headache-Related Disability Index (HDI; primary outcome) is a 25-item, self-report questionnaire of the emotional and functional impact of headache on daily activities. The items require a “yes,” “no,” or “sometimes,” response to assess participants’ perceived headache-related disability. Total scores range from 0-100; higher scores indicate higher disability.
- The Pain Catastrophizing Scale (PCS) is a 13-item self-report measure that conveys a participant’s level of pain-related, catastrophic thinking during painful experiences. The measure has three subscales: Rumination (4 items), Magnification (3 items) and Helplessness (6 items). Ratings are made on a 5-point scale from 0 (not at all) to 4 (all the time). Total scores range from 0 to 52; higher scores indicate higher catastrophizing.

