Scores are calibrated to a T score metric ($M = 50$, $SD = 10$) normed to U.S. population demographic means. Higher scores represent more severe anxiety symptoms.

6) Data Analysis

Distributions of all study variables were evaluated for normality, skewness and kurtosis. Day-level imputation was used to impute missing diary data points (15.5%) for headache diary measures. Variables at baseline were described using mean and standard deviation for normally distributed variables, and number and percent for nominal variables. Differences between treatment groups for primary and secondary outcomes at baseline were evaluated using t-tests and chi-squares.

Intent-to-treat analysis used linear (continuous variables) and logistic (dichotomous variables) mixed models for repeated measures to estimate missing values and evaluate changes in outcomes. For survey variables, time was a 4-level variable (Month 0, 1, 2, and 4); for diary data, time was a two-level variable (baseline monitoring period vs. post-treatment evaluation period). Fixed effects were group, time, and their interaction. A significant interaction indicated the slope of the MBCT-M group differed from the slope of the WL/TAU group. Random effects were intercept and time. Akaike's information criterion indicated a first-order autoregressive covariance structure was appropriate for modeling month.

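### Diary outcomes are tested by an interaction without baseline or stratum adjustment, which is unbiased but usually less precise than an adjusted analysis

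*Combined protocol and SAP*

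**What the plan says.** Section 6) Data Analysis gives one mixed-model description for all outcomes. The fixed effects are group, time and their interaction, and then "Random effects were intercept and time". Surveys and diaries are separated only by the levels of time: surveys have four, while "for diary data, time was a two-level variable (baseline monitoring period vs. post-treatment evaluation period". The treatment test is the interaction: "A significant interaction indicated the slope of the MBCT-M group differed from the slope of the WL/TAU group". On covariance, the section adds that Akaike's "criterion indicated a first-order autoregressive covariance structure was appropriate for modeling month". It does not say whether that covers the diaries, or whether the two random effects are correlated. It lists no baseline or stratum covariate.

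The Headache Diary list under Measures reduces each diary outcome to one value per month; for example, "Average day-level migraine disability (MIDI) score will be aggregated by month". Section 5) Procedure says "Participants randomized to the WL/TAU group did not take the headache diary for the 8 week treatment period", so only two diary periods are common to both arms. The same section stratifies randomisation into episodic and chronic migraine "based on headache days/month recorded in the daily headache diary", with a cut at 15 and random blocks of 2, 4 and 6. The baseline month was therefore complete before allocation.

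Section 3) Study Population gives 31 and 29 participants per arm. Under Measures, MIDAS and HDI carry the primary label; the diary outcomes do not.

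**The concern.** With one value before and one after treatment, an interaction test amounts to comparing mean changes. It subtracts the whole baseline value instead of weighting it by how well it predicts the outcome. In a trial of 60 the lost precision can matter.

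Randomisation was also stratified on a diary variable that the model omits. Stratified blocks make the arms more alike at baseline than chance would. A standard error that ignores this is too large for headache days.

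Separately, a random intercept and a random time effect fitted to two values per person can ask for more variance parameters than the data can supply.

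**Working it through.** **Inputs.** From the documents: 31 and 29 participants, two monthly values per person, stratification on baseline diary headache days, blocks of 2, 4 and 6. The documents give no diary SD, between-period correlation (rho) or power figure, so there is nothing to reproduce. Assumed: rho 0.5 to 0.8, post/baseline SD ratio k of 0.8 to 1.2, an effect of 0.5 SD, two-sided 5% tests.

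**1. What the test is.** With complete data the interaction estimate is the difference between arms in mean change. In 60 simulated fits with correlated random intercept and time, the two agreed to rounding error and no warning appeared.

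**2. Reported precision.** In units of the baseline SD with k = 1, and 1/31 + 1/29 = 0.0667:
- change-score variance = 2(1 − rho) × 0.0667
- ANCOVA variance = (1 − rho²) × 0.0667
- SE ratio, ANCOVA to change score = √((1 + rho)/2)

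| rho | change SE | ANCOVA SE | ratio | equivalent N |
|---|---|---|---|---|
| 0.5 | 0.258 | 0.224 | 0.87 | 60/0.75 = 80 |
| 0.8 | 0.163 | 0.155 | 0.95 | 60/0.90 = 67 |

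For general k the ratio is √(k²(1 − rho²)/(1 + k² − 2·rho·k)):
- k = 0.8: 0.76 to 0.80.
- k = 1.2: 0.93 to 1.00. At rho 0.8 it is √(0.5184/0.52) = 1.00, so there is no gain.

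**3. Effect of stratified blocks on headache days.** Assume a normal baseline, half the participants in each stratum, and blocks that balance the strata almost exactly. A split at the median carries 2/π = 0.637 of the baseline variance. The mean change depends on baseline with slope −(1 − rho). The design therefore removes (1 − rho)² × 0.637 from the change-score variance, and the model does not know it.

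- rho 0.5: true variance 1 − 0.25 × 0.637 = 0.841, reported as 1. True/reported SE = 0.917. Size is P(|Z| > 1.96/0.917), about 3.3%.
- rho 0.8: true variance 0.4 − 0.04 × 0.637 = 0.375, reported as 0.4. True/reported SE = 0.968. Size about 4.3%.

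Simulations with stratified blocks gave sizes of 3.0-3.5% and 4.3-4.4%.

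The ratio of actual sampling SEs is therefore milder than in step 2: √(0.75/0.841) = 0.94 at rho 0.5 and √(0.36/0.375) = 0.98 at rho 0.8. The reported SE still falls by about 13% and 4-5%, because ANCOVA also recovers the balance that the change-score SE ignores.

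**4. Power, 0.5 SD effect, k = 1, stratified blocks.** About 47% (change) against 59% (ANCOVA) at rho 0.5, and 85% against 88% at rho 0.8.

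**5. Covariance parameters (secondary).** Two values per person identify three quantities: two variances and one covariance. Correlated random intercept and time plus a residual need four. With time coded 0/1, the sets (intercept variance, time variance, covariance, residual) = (2, 0.5, 0.1, 1) and (2.5, 1.5, −0.4, 0.5) both give variances 3.0 and 3.7 and covariance 2.1. The components are not unique, but the 2×2 matrix is, and the interaction test depends only on that matrix. Uncorrelated effects with no autoregressive term need three parameters and are just identified under 0/1 coding.

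**The case against.** The strongest reply is that the stated test is valid and that preferring ANCOVA is only a choice about efficiency. Much of this stands:
- There is no bias, and the test for headache days errs on the conservative side.
- The gain rests on an undocumented correlation and SD ratio. Entry requires at least 6 diary-confirmed headache days, which truncates the baseline distribution. A larger post-treatment SD is therefore plausible, though not shown, and that is where the gain shrinks or disappears.
- The section is in the past tense and reports 15.5% missing diary points and a covariance choice by AIC. The data were in hand, so a switch to a more powerful test is a data-driven change unless it is labelled.

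None of this defends leaving out a baseline value that the trial collected before allocation, or a factor used to randomise.

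Two stronger readings are tempting. A reader might infer that the random-effects statement makes the diary test invalid, or that the fit must have failed. The documents do not support this: they do not say the effects were correlated, they interpret only the interaction, and that contrast is unaffected. The autoregressive remark refers to month, the label used for survey time, and may not concern the diaries at all.

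A reader might also extend the point to the four-visit surveys, and so to MIDAS and HDI, arguing that the autoregressive structure understates standard errors. That could matter for pairwise visit contrasts, but the plan names none.

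**Conclusion.** The point holds for the continuous diary outcomes and is mainly one of efficiency. The stated test gives an unbiased difference in mean change. It usually uses the baseline month less well than ANCOVA would, and it omits the randomisation stratum. For headache days this makes its standard error too large by roughly 9% at rho 0.5 (1/0.917) and 3% at rho 0.8 (1/0.968), under the equal-strata assumption.

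Adjustment is worth about 12 points of power at rho 0.5 and 3 at rho 0.8 with equal SDs, and nothing at an SD ratio of 1.2 with rho 0.8. It cannot be called more precise without qualification. The possible over-parameterisation is mostly missing detail: it affects the variance components and perhaps convergence, not the treatment test. The primary survey outcomes are not touched.

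**What to change.** For continuous diary outcomes, drop the random time effect. Use ANCOVA of the post-treatment month on the baseline month plus the episodic/chronic stratum. For headache days the stratum adds little beyond the baseline value itself; for severity and MIDI it brings in design information that their own baselines lack.

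Plain ANCOVA loses anyone without a post-treatment diary. The section's intention was to use "mixed models for repeated measures to estimate missing values and evaluate changes in outcomes". To keep those participants, use a two-period repeated-measures model with unstructured 2×2 covariance, the arms' baseline means set equal, and the stratum included. Without the stratum term, and with equal SDs and rho 0.5 to 0.8, its SE ratio to the unconstrained model is 0.87-0.95 with complete data and 0.89-0.96 with an assumed 6 participants per arm missing. An unstructured model that leaves the baseline means free solves the parameter count but brings no gain in precision.

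The cost is one or two degrees of freedom (58 to 57, or 56 with the stratum), a changed model statement and a rerun; no new data are needed. Because the data have already been analysed, report the adjusted result beside the existing one and label it as a change made after the data were seen. If the existing model is kept in the report, state whether its random effects were correlated and whether the autoregressive term applied to the diaries. Dichotomous outcomes use logistic models, which this change does not cover.

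### Does the unstated lag of the AR(1) structure, with surveys at unequally spaced Months 0, 1, 2 and 4, undermine the survey analysis?

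*Combined protocol and SAP*

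**What the plan says.** Section 6 (Data Analysis) states the survey schedule: "For survey variables, time was a 4-level variable (Month 0, 1, 2, and 4"). The fixed effects are group, time and their interaction, so the means are saturated. On the covariance it says "Random effects were intercept and time", and then that Akaike's criterion showed "a first-order autoregressive covariance structure was appropriate for modeling month". A significant interaction is the only efficacy signal it defines. The model is also meant to handle incomplete data: the plan speaks of "mixed models for repeated measures to estimate missing values and evaluate changes in outcomes".

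Two other places bear on the point.

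- Section 5 (Procedure) fixes the calendar. "At the conclusion of the 4-week baseline assessment period, all participants will complete psychosocial measures again"; eight weeks of treatment and four weeks of diary follow, after which "participants completed one final set of psychosocial measures through the REDCap electronic data capture system". That is 4 + 8 + 4 = 16 weeks, or four 28-day months, so the final survey is Month 4.
- Under Psychosocial Surveys, "The Migraine Disability Assessment (MIDAS; primary outcome") is described with a long recall: "Each item is an open question, allowing entry of number of days lost over 90 days".

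**The concern.** The gaps between surveys are one, one and two months. First-order autoregression gives equal correlation to pairs with equal lag. If the lag counts visits, Months 2 and 4 receive the same residual correlation as Months 0 and 1, although they are twice as far apart. Too high a correlation makes the standard error of a change too small.

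MIDAS makes this concrete. Two surveys d months apart share max(0, 90 − 28d) recall days: 62 for d = 1, 34 for d = 2, 6 for d = 3 and none for d = 4. Visit order treats the 62-day and 34-day overlaps alike, and this is a primary outcome.

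The text does not settle the lag unit, the placement (residuals or random effects), or which structures Akaike's criterion compared. At stake would be the error rate of change contrasts, the handling of missing Month 4 surveys, and whether another analyst could reproduce the model.

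**Working it through.** The plan states no standard error or correlation, so there is no figure to reproduce. All correlations below are assumed, with unit variance and d in months.

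**Rough ceiling.** The variance of a change is 2(1 − correlation). With correlation 0.7^d, the two-month change has variance 2(1 − 0.49) = 1.02 and the one-month change 2(1 − 0.7) = 0.60. Using the one-month value outright would give an SE ratio of √(0.60/1.02) = 0.77. A fitted model does better, because its correlation is a compromise over all pairs and the random time effect absorbs part of the decay.

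**Fit.** Take random intercept and linear month (correlated) plus residual AR(1) in visit order. Find the large-sample best-fitting covariance V for each true covariance S. For a contrast c, the SE ratio is r = √(c′Vc / c′Sc), and the type I error of a nominal 5% test is 2Φ(−1.96r). Sample sizes cancel from r.

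True covariances:

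- Calendar decay: 0.6^d, 0.7^d, 0.8^d, 0.5 + 0.5×0.6^d, 0.3 + 0.7×0.8^d; and, with 0.2 noise on the diagonal, 0.4 + 0.4×0.7^d and 0.6 + 0.2×0.6^d.
- MIDAS recall, R = max(0, 90 − 28d)/90, no noise: R, 0.3 + 0.7R, 0.5 + 0.5R.
- MIDAS recall with 0.2 noise: 0.4 + 0.4R, 0.6 + 0.2R.

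| SE error | Calendar decay | MIDAS, no noise | MIDAS, 0.2 noise |
|---|---|---|---|
| Month 4 − 2 | 4–12% too small | 14–15% too small | 5–8% too small |
| Month 4 − 1 | 1–2% too small | 7–8% too small | 3–4% too small |
| Month 4 − 0 | 0.5–4% too large | 5–6% too large | 1–2% too large |
| Arm difference at Month 4 | within about 1% | within 1% | within about 1% |
| Interaction, type I error | 5.0–5.3% | 5.5–5.8% | about 5.0% |

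For Month 4 − 2, r = 0.881 gives 2Φ(−1.73) = 8.4% and r = 0.961 gives 6.0%; noise-free MIDAS gives 9.2–9.4%. With an overlap that falls to zero at exactly three months, the noise-free MIDAS interaction is 5.8–5.9%. A purely stable person effect gives no error. If lags were already in months, the error is zero for the first five matrices.

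**At the trial's size** (31 v 29, complete data, 4,000 runs, Monte Carlo SE 0.3–0.5 points), the interaction test rejected in 6.1% (0.7^d), 6.1% (0.4 + 0.4×0.7^d with noise) and 6.6% (0.3 + 0.7R). On the same draws, the exact unstructured test rejected in 5.6%, 5.7% and 5.7%. The excess is 0.5, 0.4 and 0.9 points.

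**Missing data.** Assume 10–20% dropout at Month 4 driven by the Month 2 score in one arm. The Month 4 difference is biased by 0.01–0.04 SD, or up to 0.075 SD if the arms drop out in opposite directions. Its standard error is √(1/31 + 1/29) = 0.26 SD, so the bias is at most 0.075/0.26 = 0.29 standard errors, and usually 0.04/0.26 = 0.15 or less.

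**Other placement.** If AR(1) describes the two random effects, then over the first six matrices Month 4 − 2 SEs are 12–95% too large and the interaction test falls to 0.35–1.9%. That model's −2 log-likelihood is 43–110 points worse than unstructured, against 0.8–4.7 for residual AR(1). It has three covariance parameters and residual AR(1) has five, so the penalty saves it only 2 × 2 = 4 points. Akaike's criterion would not have chosen it if residual structures were compared.

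**The case for a change.** The strongest case for a change is reproducibility. Nobody can rebuild the model from this text, and the direction of error depends on a placement it leaves open. Change contrasts fall within the model's stated purpose. Month 1 is the last survey before treatment, so Month 4 − 1 is a natural pre-to-post change, and for noise-free MIDAS its type I error is about 7%. Nor does selection by Akaike's criterion vindicate visit order: in the simulated trials, month-based lags with the same five parameters had the lower value in 85%, 58% and 93% of runs (same three covariances, in the order listed above). Under other codings of random time, the Month 2 to 4 shortfall can reach 17–19%, and Month 4 − 0 can also be too small.

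The omission stands. The call for a different model does not, for four reasons.

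- Month 2 lies in mid-treatment, and change from there to Month 4 is neither a stated objective nor a named test. The 7% figure for Month 4 − 1 needs recall without any reporting error, which is hard to credit for an open-ended count over 90 days.
- If unstructured was a candidate, the reported choice of AR(1) weighs against the worst case. Under 0.3 + 0.7R, Akaike's criterion preferred the stated model to unstructured in only 19% of runs, against 85% with noise (0.4 + 0.4×0.7^d).
- The substitutes are not clean gains. Unstructured needs 10 covariance parameters instead of 5: 80% power falls to 79.1% for a single contrast and 77.9% for the interaction. Month lags with random time leave noise-free MIDAS Month 4 − 1 still 7–8% too small. Without random time, under R, Month 4 − 1 is 14% and Month 4 − 0 is 11% too small, and the interaction is 6.2% against 5.8% for the visit-order model.
- Section 6 is written in the past tense and already reports 15.5% missing diary data and the covariance selection. Replacing the main model now would be a post hoc choice.

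**Conclusion.** No change to the plan follows. Section 6 leaves out the lag unit, the placement and the candidate structures, and a fuller report would give them. But this is missing detail, not a demonstrated error.

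On the usual reading (residual AR(1) in visit order, random intercept and linear month), the harm falls mainly on a Month 2 to 4 contrast that the plan never names: 4–12% in the standard error, and 14–15% for MIDAS only without reporting noise. The named interaction test stays at about 5.0–5.9% in large samples, and runs 0.4–0.9 points above an exact test in simulations at this size. The standard error of the Month 4 arm difference is right to about 1%. Choosing unstructured instead is a fair trade-off against 1–2 points of power with 60 people. It can be reported as a sensitivity analysis, but the stated conclusion does not depend on it.

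This rests on assumed correlations and on AR(1) applying to the residuals. If it were on the random effects, the interaction test would be conservative, not liberal. The point covers the continuous survey scores only, not the diary outcomes or the logistic models.
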